1.0 Study Summary

The confluence of obesity and pre-diabetes in older adults substantially increases the risk of diabetes, and accelerates functional decline, multimorbidity, disability, and death. More research is needed to refine and extend preventive interventions to reduce burden for elders and society. For over a decade efficacious 6- and 12-month Diabetes Prevention Program (DPP) based lifestyle interventions have been translated successfully and demonstrated positive impact. However, efforts to develop and evaluate more scalable programs conforming to current Medicare guidelines (MDPP) for longer term DPP interventions (up to 18- or 24-months) and help a greater proportion of enrollees achieve and sustain the recommended weight loss target of $\geq 5\%$ are lacking. Our scientific premise is that the evaluation of translational DPP interventions, which has centered largely on strategies for weight loss induction, must be extended to include longer-term interventions that clearly demonstrate durable weight, cardiometabolic and functional health benefits for vulnerable elders in community-based settings. Our previous DPP-adapted research has documented the utility of group telephone follow-up after a 6-month DPP weight loss induction and shown that 63% of a 65–80-year-old volunteer sample with obesity and other risk factors were able to sustain $\geq 5\%$ weight loss at 12-months.

Despite good evidence that longer duration lifestyle interventions yield better outcomes (reflected in recent Medicare rulings) translational studies of 24-month long DPP interventions with older adults are scarce. This study utilizes community-based settings to examine whether we can sustain the impact of an elder-focused DPP approach using potentially scalable telehealth treatment components over a 24-month period. We will recruit and enroll 65–80-year-old adults with obesity and pre-diabetes (N = 360) through networks of senior community centers that provide aging services and utilizing other older adult targeted database resources. The intervention program sequencing will be aligned with current Medicare (MDPP) policy. First, from 0-6 months, experienced lifestyle coaches will offer a DPP-video intervention anchored by group telephone coaching for all participants, at least 25% from ethnic/racial minority groups. Next, participants, will be randomized (up to N = 180 per arm; stratified by weight loss of < or $\geq 5\%$) to one of two 18-month follow-up conditions conducted between 6-24 months. We will compare the effects of (1) DPP-Behaviorally Intensive 30-Minute Groups or DPP-BI and (2) DPP Minimal Support 15-Minute Groups or DPP-MIN on measures of weight/adiposity (the primary outcome) at 12, 18, and 24 months. In addition, we will collect cardiometabolic, physical activity, physical function, psychosocial, behavioral, and other age-sensitive quality of life measures at these same intervals. Medicare claims data will be examined for a proportion of the sample, regarding types of medical utilization. If successful, this work will have immediate potential for MDPP lifestyle interventions, involving telehealth delivery, which are consistent with a chronic care model, and will benefit vulnerable aging individuals and society.

2.0 Objectives

Obesity in adults ≥ 65 years is prevalent¹⁴ and elevates risk for diabetes,¹⁵ multimorbidity,¹⁶ functional decline¹⁷ and healthcare burden.¹⁸⁻²⁰ The Diabetes Prevention Program (DPP) intensive lifestyle intervention²¹⁻²⁴ has been translated successfully by our group^{5,25-28} and others²⁹⁻³¹ using primarily 6- or 12- month in-person programs, but translational studies have been hampered by lack of scientific rigor, incomplete reporting, inadequate focus on behavioral intensification for participants not meeting goals, and lack of scalable, longer duration interventions.³¹ Because there is good evidence that achieving and sustaining clinically meaningful weight loss of $\geq 5\%$ ³²⁻³⁴ over time is critical for durable health benefits, especially for vulnerable elders with obesity and pre-diabetes,^{23,35,36} longer term tests of DPP-based behavioral self-management interventions are needed. These findings could have immediate

Reducing cardiometabolic risk and promoting functional health in community-based elders with obesity and pre-diabetes: evaluating sustainable follow-up strategies

impact for the increasing number of state and national DPP programs being designed to meet the chronic healthcare needs of the Medicare population.^{1,37}

Our central scientific premise is that DPP programs and associated benchmarks have been well-established for the 6 month weight loss induction intervention, but that the most effective strategies for conducting longer duration DPP interventions with vulnerable older adults in the community are lacking.^{31,38} Our research group is well-qualified to develop and evaluate such an approach. We have shown that a 12-session, face-to-face, DPP intervention for elder volunteers followed by 6 months of modest interactive group phone support (one 30-minute contact/month) was associated with significant weight loss²⁸ ($7.5 \pm 5.5\%$ and 63% achieving $\geq 5\%$) and associated health improvements at 12 months. Now we propose to extend our previous work to senior community center settings and test more scalable intervention strategies, in a two-arm trial, designed to achieve and sustain weight losses of $\geq 5\%$ and produce cardiometabolic, physical function, and other health benefits over 24 months.

The proposed translational effectiveness study will commence with a non-randomized, video-delivered DPP intervention (our Group Lifestyle Balance-DVD)^{4,25} anchored by telephonic group contact as a lower-cost model for achieving the primary weight loss induction of $\geq 5\%$, followed by randomization to either DPP-BI or DPP-MS (both telephonic coaching interventions, both aligned with a Medicare delivery schedule) for the next 18 months. After the 6-month induction period, participants will be stratified by weight loss achievement ($<$ or $\geq 5\%$) and those assigned to DPP-BI will receive continued MDPP-prescribed behavioral group sessions (remotely) plus additional individualized activity coaching. Activity is critical at any age, but for elders with obesity and pre-diabetes, especially those who have not reached DPP weight targets by 6-months, it may enhance cardiometabolic and functional health outcomes compared to minimal contact alone.^{7,39} Between 12-24 months the DPP-BI group will continue with group phone coaching sessions that are designed to integrate DPP weight management strategies with those aimed at critical self-care/healthcare behaviors for healthy aging (“5-keys”)^{8,10}. In contrast, those assigned to DPP-MS (control) will rely on brief group phone contacts alone *as the minimum scalable modality* for lifestyle behavior change accountability over this period.

We plan to recruit and enroll ambulatory adults, 65 years of age and older (up to N = 360) with BMI $\geq 27 \text{ kg/m}^2$ and pre-diabetes (FPG ≥ 100 and $< 125 \text{ mg/dl}$, or HbA1c ≥ 5.7 and $< 6.4\% \text{ mg/dl}$) from senior community settings and using other database resources. Between 0-6 months, a base DPP intervention of self-directed lifestyle change videos, activity videos, and weekly group phone contact (16 sessions) will be provided to all enrolled. Between 6-12 months, individuals randomized to DPP-BI, will receive DPP sustained DPP-BI 30-minute group calls (6 sessions) and ≤ 2 individual physical activity consults. Between 12-24 months sessions reduce to one every two months (6 sessions). Those assigned to DPP-MS, will participate in brief unstructured group support phone contacts according to the same schedule. Participants, 25% from ethnic/racial minority groups (primarily African American), will be assessed at baseline, 6, 12, 18, and 24 months to determine the following specific aims:

Aim 1: Document the impact of DPP-BI compared to DPP-MS on weight at 12, 18, and 24 months.

Hypothesis 1: Overall, DPP-BI compared to DPP-MS will result in more favorable weight loss (average change and the proportion reaching $\geq 5\%$) at 12, 18, and 24 months.

Aim 2: Document the impact of DPP-BI compared to DPP-MS on cardiometabolic, physical activity/function, secondary outcomes, and behavioral adherence measures at 12, 18 and 24 months.

Hypothesis 2: Overall, DPP-BI compared to DPP-MS will result in more favorable cardiometabolic, physical activity/function, secondary outcomes, and behavioral adherence measures at 12, 18, and 24 months.

Reducing cardiometabolic risk and promoting functional health in community-based elders with obesity and pre-diabetes: evaluating sustainable follow-up strategies

Exploratory Aim: We will examine differences in intervention response (weight, cardiometabolic, and function) by race (African American, Caucasian). For a proportion of the sample, we will explore Medicare data for group differences in medical utilization (medications, outpatient, inpatient, emergency visits) and participation in activity programs.

Evaluating incremental refinements to standard DPP approaches through community centers providing aging services, in alignment with MDPP^{1,37} and other Medicare subsidized activity benefits, will improve our understanding of the most effective and potentially sustainable long term approaches for weight control and health maintenance in vulnerable older adults. A successful demonstration of 12-, 18- and 24-month interventions using video- and telephone-coaching strategies to sustain weight loss self-management and enhance behavioral activation for cardiometabolic control and functional health outcomes would have significant individual and public health benefit.

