Continued Group Teleconference Coaching for the Active Comparator and the Placebo Comparator (6-24 months). Following the six-month assessment visit, randomization to one of the two 18-month continued contact conditions followed stratification by weight loss achievement of < or \geq 3.5%, and also incorporated age, sex, and race as balancing variables. The two conditions are: (Active Comparator) DPP Behaviorally Intensive or DPP-BI:30-Minute Calls (monthly) and (Placebo Comparator) DPP Minimal Support or DPP-MIN:15-Minute Calls (monthly). Both group conditions have the same follow-up dose/frequency (total of 18 group contacts) and each cohort meets with the same lifestyle coach as they did during their base sequence.

The DPP-BI condition was designed to be behaviorally intensive and aligned with principles of MDPP implementation. Structured workbooks were used to guide all DPP-BI sessions. In addition, those assigned to this arm were offered up to 2 additional one-on-one phone consultations with a Masters-level physical activity specialist for tailored guidance and feedback on their activity goals between Sessions 18 and Session 20. Subsequent DPP-BI sessions incorporated concepts from the “5-Keys to Healthy Aging” and integrated self-care/healthcare for blood pressure, blood glucose, LDL cholesterol, healthy bones, muscles and joints, and mood (depression). Such health maintenance and weight loss maintenance health goals were mutually reinforced during this phase. Lifestyle coaches followed a standardized leader guide and session scripts. Phone sessions were designed to last about 30 minutes and the protocol dictated not to exceed 45 minutes.

The DPP-MIN condition was designed to provide brief, unstructured phone contacts that rely on the group members sharing and discussing their successes and challenges of the past month with minimal input from the Health Coach. There are no workbooks, or self-monitoring materials provided. Each session lasts about 15 minutes. Lifestyle coaches did not present new intervention material, nor did they follow a standardized script for delivering session content. They used group facilitation prompts such as noted in Table 1.

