Analysis Plan for Hypotheses 1 and 2: We will apply mixed effect models to evaluate differential changes in weight measures at 6, 12, 18, and 24 months from baseline, with fixed terms of group (DPP-BI vs. DPP-Min), time as a factor (6,12,18, and 24 months), and the group by time interaction. We employed the following steps as the pre-randomization balancing logic: (1) group subjects by weight loss status (≤ 3.5 vs. > 3.5 percent at 6-months) and age (≤ 70 vs. > 70 years at baseline), (2) group subjects by sex (male vs. female) and race (Black/African American or Black/Mixed/Other vs. White/Caucasian), (3) group subjects using all 4 factors (based on 2x2 frequency table) and (4) randomly assign the subjects in the same cell into 2 conditions (DPP Plus vs. DPP Minimal). Subject was included as a random term. To test the differential treatment effect, evaluated the coefficients that are associated with the group and the group by time interaction by using an F test. Planned contrasts will be set up from the mixed models to compare the improvement in weight from baseline to Months 12, 18 and 24 between the two conditions (DPP-BI vs. DPP-Min). In addition, a generalized mixed-effect model was fit to the binary outcome of achieving $\geq 5\%$ weight loss at 6, 12, 18, and 24 months, with the logit link, which includes similar fixed and random terms as above. Average percent weight loss and the proportions achieving $\geq 5\%$ weight loss are compared between the two groups at 12, 18 and 24 months. Similar analyses were performed for fasting glucose, HbA1c, and insulin (and other biometric measures), physical activity/function, and other secondary outcomes at subsequent assessment points.

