The planned contrasts were set up to compare differential changes from baseline to Months 12, 18, and 24. Benjamini-Hochberg's method was used to control for the overall type I error for multiple secondary outcomes. More intensive modeling is performed to account for factors that are known to affect the outcomes as well as those that have been found to differ between treatment conditions at baseline and at Month 6 (the timepoint at which participants are stratified by $<$ or $\geq 3.5\%$ weight loss and other factors and randomly assigned to the two 18-month conditions). We also perform analyses in which we restrict our linear and generalized mixed-effect analyses to those who did not reach $\geq 5\%$ weight loss at 6 months and set up the contrasts to compare DPP-BI with DPP-MIN, on average, and the proportion reaching $\geq 5\%$ at 12 months and 18 months from baseline.

Exploratory Aim. We examine available Medicare data for those insured by a large regional payer to assess group and time from baseline differences in medical utilization metrics (e.g., type of outpatient, inpatient, or emergency visits) and participation in activity programs, for a proportion of the sample. We will extract Medicare data on numbers of outpatient, inpatient and emergency visits, and number of subjects participating in activity programs, and compare the numbers between the two conditions using linear and generalized regression models. We will explore the potential moderation effects of sex and race. We will include the interaction of sex by group or race by group in the mixed-effect models, as well as the three-way interaction of sex, group and time or race, group and time, if the group by time interaction is significant in the original model.

Reducing cardiometabolic risk and promoting functional health in community-based elders with obesity and pre-diabetes: evaluating sustainable follow-up strategies

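### The protocol gives two cuts, 5% and 3.5%, for the Month-6 randomization stratum, and the mixed models do not commit to that stratum as a term

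*Protocol*

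**What the plan says.** Two places in the protocol put the cut at 5%. Section 1.0 describes randomization as "stratified by weight loss of < or $\geq 5" per cent, and Section 2.0 says "participants will be stratified by weight loss achievement ($<$ or $\geq 5" per cent.

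The other places put it at 3.5%. In Section 5.0, randomization "followed stratification by weight loss achievement of < or \geq 3.5" per cent, "and also incorporated age, sex, and race as balancing variables". In Section 18.0 the first balancing step is to "group subjects by weight loss status (≤ 3.5 vs. > 3.5 percent at 6-months", crossed with age. The paragraph that follows describes participants as "stratified by $<$ or $\geq 3.5\%$ weight loss and other factors". The SAP repeats both Section 18.0 forms.

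For the analysis, Section 18.0 and the SAP name group, time (6, 12, 18 and 24 months) and group-by-time as fixed terms, with subject as a random term. Both then plan to restrict the "mixed-effect analyses to those who did not reach" 5%; the subset is "those who did not reach $\geq 5\%$ weight loss at 6 months". The contrasts for this subset are at 12 and 18 months.

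**The concern.** The stratum defines the allocation, so it has to be reported correctly and is the first candidate for a model covariate. As written, someone who lost 4.2% by Month 6 is in the lower stratum under Sections 1.0 and 2.0 and in the upper stratum under Sections 5.0 and 18.0 and the SAP. No current text explains the change of cut. An analyst who wants to add the stratum cannot tell from the documents how to code it.

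The choice also affects how the restricted analysis is described. With a 5% cut, the below-5% subset would be exactly one randomization stratum. With a 3.5% cut it straddles two. Section 2.0 singles out people who miss the weight target by Month 6, so readers will look at this analysis and may assume that it follows a stratum.

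**Working it through.** **1. The rule, place by place**

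| Place | Cut | Exactly at the cut |
|---|---|---|
| Protocol 1.0 | 5% | upper stratum |
| Protocol 2.0 | 5% | upper stratum |
| Protocol 5.0 | 3.5% | upper stratum |
| Protocol 18.0, balancing steps | 3.5% | lower stratum |
| Protocol 18.0, following paragraph | 3.5% | upper stratum |
| SAP, balancing steps | 3.5% | lower stratum |
| SAP, following paragraph | 3.5% | upper stratum |

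There are two cuts and, at 3.5%, two boundary conventions. The second matters only for someone at exactly 3.5%.

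**2. Whether a stated figure depends on the cut**

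Inputs from the power paragraph of Section 18.0: 180 per arm, 90% at Month 12 (worded as attrition), effect size 0.31, two-sided 0.05.

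- Reading 90% as retention, n = 180 × 0.90 = 162 per arm.
- Power = Φ(0.31 × √(162/2) − 1.96) = Φ(2.79 − 1.96) = Φ(0.83) = 0.797. The noncentral t gives 0.794. The stated 80% is reproduced.
- Detectable effect = (1.96 + 0.84) × √(2/162) = 0.311, as stated.
- Expected effect = (7.5 − 5.5)/5.8 = 0.345, matching the stated 0.34.

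The cut is not an input to any of these.

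**3. How many people lie between the cuts**

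The documents give no Month-6 distribution. Assume a normal one with mean μ = 4 to 7% and SD σ = 5.5 to 5.8%. Those SDs come from Sections 2.0 and 18.0 and are 12-month values borrowed for Month 6. Take 360 × 0.90 = 324 people at Month 6, using the 90% retention in Section 18.0.

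- Share between the cuts = Φ((5 − μ)/σ) − Φ((3.5 − μ)/σ).
- Example, μ = 5 and σ = 5.5: 0.500 − 0.3925 = 0.1075; × 324 = 35 people; 0.1075/0.500 = 21.5% of the below-5% subset.
- Over the range: 9 to 11% of participants, 30 to 35 people, 18 to 27% of the subset.
- Widening to means of 4 to 7.5% and SDs of 4.5 to 5.8%: 9 to 13%, 29 to 43 people, 18 to 35% of the subset.

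This counts the people affected by the ambiguity. It does not measure an effect on any result.

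**4. Whether the 3.5% cut harms balance in the below-5% subset**

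Simulation: 324 participants, the means and SDs of step 3 (first range), half of each stratum to each arm, 4,000 runs per setting, other balancing factors ignored. The measure is the difference between arms in the share of the below-5% subset that lies between 3.5% and 5%.

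- 3.5% cut: SD of the difference 4.7 to 6.6 percentage points.
- 5% cut: SD 5.7 to 8.3 percentage points.
- Mean difference about zero under both.

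The 3.5% cut does slightly better on this measure. A 5% cut fixes the arm sizes below 5% but leaves the mix within that group to chance.

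**5. Whether the stratum is in the models**

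The named fixed terms do not include it. Section 18.0 and the SAP mention adjustment for race, sex, age and other baseline variables. They also plan further modeling of factors known to affect the outcome or found to differ between arms at baseline and Month 6. Neither statement commits to the weight-loss stratum.

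**The case against.** The strongest reply is that this is leftover proposal wording. Sections 1.0 and 2.0 are written in the future tense; Sections 5.0 and 18.0 report the allocation largely in the past tense, and they and the SAP all say 3.5%. On that reading there was one rule and the front matter was not updated. This is likely, and it disposes of one tempting inference, that staff following different sections would allocate the same participant from different cells. The documents show no sign of two rules in use. The text still needs correcting, and the boundary conflict lies within the operational sections themselves.

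A second reply is that adjustment is already foreseen. In part it is: the sentence just before the restricted analysis mentions Month-6 differences and identifies Month 6 as the time of stratification. But it leaves the choice of covariates partly to what is found to differ, and it does not name the stratum.

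A reader might also infer that a subset cutting across strata is poorly balanced or biased. The documents do not support this. Month-6 loss is known before allocation, so the restricted comparison is still between randomized groups, and step 4 shows no loss of balance between 3.5% and 5%. The 3.5% cut gives up only equal arm sizes below 5%, a minor matter of efficiency. A 5% subset is also a legitimate choice, since 5% is the program's benchmark.

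**Conclusion.** The point holds as an inconsistency in the randomization rule together with an uncommitted model term. The 5% and 3.5% cuts both stand in the current protocol, and the 3.5% boundary is written two ways. The weight-loss stratum is not a committed term in the main models or in the below-5% models.

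No comparison is biased, and the 80% power stands. The price is that the allocation cannot be described or coded with certainty from the documents, and that precision from a prognostic design factor may go unused. That gain cannot be sized, because the documents give no correlation between Month-6 and later weight loss. The count of 30 to 35 people between the cuts rests on an assumed normal distribution with borrowed SDs, and should be read only as showing that the ambiguous group is not trivial.

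**What to change.** 1. Confirm from the randomization program which cut and which boundary convention were used.
2. State that one rule in Protocol Sections 1.0, 2.0, 5.0 and 18.0 and in the SAP. If 3.5% was used, Sections 1.0 and 2.0 change, and the remaining places are made to agree on where exactly 3.5% falls.
3. Add the weight-loss stratum, coded as at randomization, as a fixed term in the mixed models, and in particular in the below-5% models. Continuous Month-6 weight loss is an alternative only where Month 6 is not itself a modeled outcome. The main models include Month 6 in the time factor, so the stratum is the simpler choice there.
4. If 3.5% was used, say that the below-5% subset does not coincide with a randomization stratum. A contrast within the lower stratum could be reported beside it, but this is optional.

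The cost is a few wording changes and one model term. No new data are needed, and the sample size and primary comparison do not change.

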3.0 Background

Expanding on our previous work, we argue for employing an elder focused, behaviorally robust 24-month DPP³⁷ lifestyle intervention. With Medicare reimbursement for group lifestyle intervention now available, including virtual delivery options, but scant data regarding the most effective, sustainable weight-loss maintenance strategies, we conclude that refining and evaluating longer term healthy lifestyle maintenance programs for elders in the context of existing senior services can propel advances in preventive healthcare and potentially decrease medical burden for older adults and society.

Obesity is prevalent in the aging population and associated with cardiometabolic risk. By 2030 over 20% of the residents of the United States (US) will be over the age of 65⁴⁰ and obesity in this group is likely to have critical implications for 21st century population health. Increases in obesity (BMI ≥ 30 kg/m²) among adults in all age groups have neither slowed nor stopped.¹⁴ According to the US Centers for Disease Control and Prevention (CDC) National Health and Nutrition Examination Survey (NHANES) reports⁴¹⁻⁴³ more than one-third of men and women ≥ 60 years have obesity. Women compared to men, aged 65-74, have the highest obesity prevalence rate among older adults at 44.2%. Obesity prevalence rates have been shown to fall by roughly 10% after age 75, although black women and individuals in rural communities⁴⁴ continue to demonstrate high rates of obesity well into late life. Moreover, many cross sectional and prospective studies of elders have shown the adverse health consequences of excess adiposity for metabolic, cardiovascular and general health outcomes (e.g., hyperglycemia, metabolic syndrome, insulin resistance, diabetes, inflammation, plasma lipids, arterial blood pressure, and other downstream physiologic abnormalities).⁴⁵⁻⁴⁸ Uncontrolled hypertension, dyslipidemia, and cardiovascular disease have decreased over the last few decades in all BMI categories, including among obese adults, however diabetes has not.^{49,50} Epidemiologic studies, such as the prospective Cardiovascular Health Study, have provided compelling evidence⁵¹ that high BMI, central adiposity or weight gain during the period of ages 65-74 years is associated with increased diabetes risk.^{15,52} The problem of obesity and diabetes is increasing throughout the lifespan in the US, but absolute prevalence rates of diabetes remain highest among adults aged 65-79 years⁵³ owing to increasing incidence and decreasing mortality.⁵⁴ Thus, this is a critical period for weight management and health promotion activities.

Obesity and diabetes in aging individuals accelerate risk for functional health decline. In addition to its association with cardiometabolic risk, obesity is consistently shown to be one of the top 2-3 modifiable risk factors for osteoarthritis and mobility disability in older adults.^{17,55-57} Data from NHANES and Medicare research have shown that obese older adults are more likely than their normal weight counterparts to report problems with walking, using stairs, and lifting.⁵⁸ Although some investigators have argued that obesity is inversely associated with morbidity and mortality in elders (i.e.,

Reducing cardiometabolic risk and promoting functional health in community-based elders with obesity and pre-diabetes: evaluating sustainable follow-up strategies

the “obesity paradox”),^{59,60} the CDC and many medical and scientific organizations⁶¹ have recommended that older individuals with obesity be identified, evaluated and treated with prudent lifestyle intervention strategies given the burden of comorbidities and accelerated functional decline likely to negatively impact life expectancy and quality of life.^{45,62-64} In addition, normative age-related physiologic changes are associated with a progressive loss of lean muscle mass and function known as “sarcopenia” with prevalence estimates ranging from 25-50% of adults ≥ 65 years showing problems with body strength and endurance.⁶⁵ The term “sarcopenic obesity” has been coined to describe the problematic interplay of excessive fat mass and low muscle function. Functional decrements may operate through biomechanical pathways (e.g., lower extremity stress and pain) or through cardio-metabolic and pro-inflammatory pathways, all of which contribute to poor health outcomes. Although some have argued that weight loss among older adults may result in further loss of lean mass and compromise functional health,⁶⁶ several intervention studies have shown that sustained modest weight loss, particularly when combined with regular physical activity, is highly beneficial.^{3,67,68} Additional research that indicates it is the confluence of obesity and diabetes that accelerates the physical function impairment and reduced quality of life seen in aging individuals, is especially pertinent to the current proposal.^{45,62,63,69,70} Unless feasible and sustainable prevention efforts are mounted^{3,63,64} an increasing number of aging adults will be living longer with obesity and the progressive burden of chronic conditions and mobility impairment.

Obesity, diabetes, and mobility disability accelerates loss of independent living. It has been documented that the average age of nursing home residents with obesity is 74, compared to age 80 for normal-weight residents⁷¹. Although serious deficits in activities of daily living and disability (e.g., getting in and out of bed, eating, and dressing independently) have decreased during the last decades of the 20th century overall, they have increased by 43% for those living with obesity⁵⁸. A large prospective study⁷² of community dwelling elders, aged 65-74 at baseline, examined the odds of nursing home admission over 2 decades and found that obesity increased the risk of admission by roughly 30%; obesity plus one additional risk factor (diabetes, hypertension, or smoking) doubled the odds. Maintaining functional independence is certainly paramount to older adults, caregivers, and the healthcare system. Thus, mitigating obesity and diabetes risk during this period seems particularly crucial for delaying the onset of more costly and restrictive levels of care.

Older adults respond well to diet and activity interventions but have been underrepresented in major clinical trials and community-based studies. Elders typically comprise <20% of the enrolled sample in major multicenter weight loss trials, but available data indicates they are very responsive to the behavioral regimens provided.^{23,36,73} This was striking in the DPP trial, with individuals ≥ 60 years attending more sessions (including supervised group activity), self-monitoring more consistently, achieving weight loss of $\geq 7\%$ ⁷⁴ and increasing physical activity³⁶ at higher rates than younger participants. This observed outcome was associated with a decrease in incident diabetes of 71% over an average 34 months of active follow-up compared to the average decrease of 59% (ages 45-59) and 48% (ages 25-44) in the younger age groups. Figure 1a and 1b suggest that the long period of sustained weight loss (left, bottom line) among older adults was critical to diabetes prevention/delay (right, bottom line) compared to the metformin (middle line) and placebo (upper line) groups. However, older adults have not been the focus of most translational studies of DPP interventions and other cardiovascular risk intervention trials⁷⁵ and Medicare coverage decisions have often been extrapolated from younger persons. A translation study by West et al⁷⁶ delivered in senior centers by lay health workers compared a 12-session DPP intervention to an attention control program and found significant differences between groups, but weight loss did not reach 5% on average. More community studies evaluating longer duration programs are needed to document the full potential for meaningful weight and health outcomes.

Reducing cardiometabolic risk and promoting functional health in community-based elders with obesity and pre-diabetes: evaluating sustainable follow-up strategies

Weight management and other evidence-based lifestyle interventions such as “10- Keys™ to Healthy Aging” have potential to mitigate multiple chronic conditions in aging adults.

Epidemiologic data show that older adults who maintain ≥ 4 healthy lifestyle habits (e.g., faster walking pace, more leisure physical activity, modest alcohol intake, BMI <30 kg/m² and not smoking) have 45% lower odds of incident heart failure.⁷⁷ Several large randomized trials of intensive diet and activity interventions demonstrate that weight loss in the 65+ age group with obesity also results in enhanced health related quality of life, vitality and physical function.^{64,68,78,79} Moreover, in addition to cardiometabolic and musculoskeletal impact, obesity has been associated with an approximate 25% increase in odds of mood and anxiety disorders, including among adults ≥ age 60⁸⁰. A community intervention study⁸¹ of racially diverse older adults found that either a brief evidence-based problem solving therapy directed at mood regulation, or an individual nutrition coaching program directed at healthy lifestyle, performed equally well in reducing symptoms of depression over 24 months among elders with elevated depressive symptoms at baseline. Our GLB intervention (mean age 72) also demonstrated a “two-for-one” (weight loss and mood) benefit in the short term²⁸. Therefore, our scientific premise is that older adults, at ever increasing risk for multiple chronic conditions,^{16,18,82} may benefit from comprehensive behavioral lifestyle interventions that reinforce common self-management behaviors (i.e., goal-setting, self-monitoring, problem-solving) with capacity to address multiple risk factors. Indeed, this is the theoretical rationale for the development of elder-focused approaches such as “10- Keys to Healthy Aging”,⁸ and is wholly consistent with DPP intervention goals regarding the importance of maintaining a healthier weight for cardio-metabolic and functional health benefit. With the proposed study of longer duration maintenance interventions, we reason that integrating DPP-based weight maintenance and a “multimorbidity prevention” approach is synergistic, with potential to amplify motivation for self-care among elders.

Few DPP translational studies have documented longer term maintenance outcomes or moderators of success beyond 12-months. We know from clinical trials, overall, that continued contact,⁸³ self-monitoring,⁷⁴ self-weighing,⁸⁴ problem solving,⁸⁵⁻⁸⁷ and adherence to physical activity are all implicated in the maintenance of long term weight loss and associated cardiometabolic and physical function benefits⁸⁸. However, a recent meta-analysis of 44 DPP-based translation/dissemination studies demonstrated that a gap exists between that which has been demonstrated by obesity treatment efficacy research and DPP translational findings. Although short-term cardiometabolic benefits are evident, this systematic literature review found that the average number of program contacts in the first six months of DPP translational studies was 11 sessions and only 60% included a continued contact program of any kind. Moreover, translational programs that have offered follow-up interventions have reported that in-person attendance wanes significantly during the second six months of programming and may not be cost-efficient.⁸⁹ Thus, it appears critical that future studies address the feasibility and effectiveness of different strategies and formats for retaining participants to longer duration interventions, particularly after the initial period of weight loss induction to mitigate the likelihood of weight regain and loss of health benefits. Primary care based DPP translations have begun to examine the use of web-based⁹⁰ and telephonic support⁹¹ to promote maintenance of weight loss and cardiometabolic improvements but these approaches have not been examined long term with elders, nor has the study of elder-focused physical activity programming and guidance been integrated or evaluated.

Enrollment/participation in community-based activity programs is a potentially promising approach for enhancing weight loss maintenance and functional health in elders. King and Guralnik⁹² have argued that the best way to maintain functional health in an aging population is to increase their physical activity and social engagement; providing behavioral guidance for community-based activity program participation may offer a means to both ends. To date, most DPP interventions

Reducing cardiometabolic risk and promoting functional health in community-based elders with obesity and pre-diabetes: evaluating sustainable follow-up strategies

have focused on self-monitoring and awareness of activity minutes or steps but not necessarily the merits of enrolling in structured or supervised activity programs. Increasing behavioral support for appropriate activity programs has potential to improve the weight and health of elders with cardiometabolic risk, such programs are often part of the services provided at senior centers and fitness facilities but are underutilized. Importantly, prospective research has shown that adjusted Medicare costs decreased in the two years subsequent to joining these types of activity programs (e.g., Healthways Silver Sneakers®, Silver&Fit®, EnhanceFitness®)⁹³. Other data suggests that program participation of ≥ 1 time per week is related to lower adjusted health care costs at 12 and 24-months post enrollment,^{94,95} compared to controls. However, less is known about the factors associated with joining or adhering to Medicare subsidized physical activity programs. Focus group data from a large health maintenance organization has suggested that non-users, compared to users, have more physical limitations due to health conditions and aging and want more professional guidance on how to adapt physical activity regimens.⁶ Facilitators of enrollment included motivation to maintain physical strength, independence, and mental health, engaging and knowledgeable instructors, and the social camaraderie of certain programs and gyms. No studies, to our knowledge, have examined the impact of these types of elder-focused activity programs when combined with a structured weight loss/weight maintenance component.

Our own initial internal review of Silver and Fit™ data, the subsidized activity program for elders that is part of the UPMC Health Plan, indicated that in 2015 only about 12.5% of those enrolled in Medicare Advantage chose to participate in this activity benefit. For those who did elect to participate, most attended classes < 3 times per month. Undoubtedly, there will be considerable variability in the activity needs, preferences, and outlets that best serve a 65–80-year-old cohort with obesity, pre-diabetes and emerging chronic conditions. However, we argue that comparing the effectiveness of a weight loss maintenance intervention that incorporates physical activity program guidance, compared to a minimal contact control, has potential to advance our understanding of effective lifestyle weight management strategies and outcomes.

